4.10.8. Subgroup Analyses on Primary and Secondary Efficacy Endpoints

Subgroup analyses of the primary and secondary endpoints will be performed in the same manner as the primary analysis within each of the following subgroups based on the FAP:

- Baseline Age (≤ 6.0 years old and > 6.0 years old)
- Baseline Time to Stand from Supine (≤ 5 seconds and > 5 seconds)
- Region (North America and Europe/Asia/Australia).

The MMRM model for the previous treatment with eteplirsen subgroup will be the same as the main model. The MMRM model for the other subgroups will be the same as the main model, excluding the subgroup as a factor. If particular subgroups have too few observations (patients) to provide a meaningful MMRM analysis, then descriptive statistics only will be presented for those particular subgroups.

Note that these analyses will be performed on the randomization strata.

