4.2. General Statistical Methods and Data Handling

4.2.1. General Methods

Tabulations will be produced for appropriate demographic, Baseline, efficacy, and safety parameters. For categorical variables, summary tabulations of the number and percentage within each category (with a category for missing data) of the parameter will be presented. For continuous variables, the mean, median, standard deviation, minimum and maximum values will be presented. Unless otherwise defined for a particular endpoint, a patient's Baseline value is defined as the last non-missing measurement prior to the initiation of study drug. The first day of study drug is "Day 1".

Formal statistical hypothesis testing will be performed on the primary and secondary efficacy endpoints ([Section 2.5.1](#)), with all tests conducted at the 2-sided, 0.05 level of significance. Summary statistics will be presented, as well as confidence intervals (CIs) on selected parameters, as described in the sections below.

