4.2.5. Multiplicity

The following multiplicity adjustment approach will be used to strongly control the overall Type I error rate at 0.05 (two-sided) for the primary endpoint and three secondary endpoints.

A hierarchical testing procedure will be used for the secondary endpoints. At each step the test for treatment effect will be considered statistically significant if the p-value is less than or equal

to 0.05 and all previous tests also meet this level of significance. The testing hierarchy is as follows:

1. Primary endpoint: CFB in the NSAA Total Score at Week 52
2. Secondary endpoint: CFB in the Stand from Supine Speed at Week 52
3. Secondary endpoint: CFB in the 10MWT Speed at Week 52
4. Secondary endpoint: CFB in the 4-Stair Climb Speed at Week 52

This method provides strong control of the family-wise error rate at the 2-sided 0.05 level.

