4.2.6. Subgroups

Primary and secondary efficacy analyses will be performed within each of the following subgroups based on the FAP:

- Baseline Age (≤ 6.0 years old vs. > 6.0 years old)
- Baseline Time to Stand from Supine (≤ 5 seconds vs. > 5 seconds)
- Region (North America vs. Europe/Asia/Australia)

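### Subgroups are assessed only by separate within-level tests, so the SAP cannot show whether the treatment effect differs by age, time to stand or region

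*SAP*

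**What the plan says.** SAP 4.2.6 announces the subgroup work: "Primary and secondary efficacy analyses will be performed within each of the following subgroups based on the FAP". It lists age (cut at 6.0 years), time to stand from supine (cut at 5 seconds) and region (two groups). SAP 4.10.8 repeats the list and sets the method: "Subgroup analyses of the primary and secondary endpoints will be performed in the same manner as the primary analysis within each of the following" level. On the model it says: "The MMRM model for the other subgroups will be the same as the main model, excluding the subgroup as a factor". Where a subgroup is too small for a meaningful MMRM, "then descriptive statistics only will be presented for those particular subgroups"; no size threshold is given. The analyses use the randomization strata.

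The primary analysis in SAP 4.10.1 reports LS-means differences with p-values and 95% CIs, so the subgroup runs inherit p-values. Section 4.10.8 states no significance level. The nearest statement is in SAP 4.2.1, on formal testing of the primary and secondary endpoints: "with all tests conducted at the 2-sided, 0.05 level of significance".

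SAP 4.2.5 aims to "strongly control the overall Type I error rate at 0.05 (two-sided) for the primary endpoint and three secondary endpoints" through a four-step sequence and does not mention subgroups. Protocol 9.16.3 leaves subgroups to the SAP.

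**The concern.** A subgroup analysis should answer whether the effect differs between, say, younger and older boys. Only a comparison of the two effects answers that. The subgroup model is fitted inside one level at a time, so it cannot hold a treatment-by-subgroup term, and the SAP text has no interaction test elsewhere. The reader is left with pairs of p-values.

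Two misreadings follow. If the trial succeeds, a factor with one significant and one non-significant level looks like a drug that works only in some boys, although half-size samples produce that pattern readily when the effect is uniform. If the trial fails, a nominally significant subgroup invites a claim. Neither section calls these results exploratory, nominal or descriptive.

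**Working it through.** **Inputs from the documents.** SAP 4.1: about 126 boys, 2:1, effect size 0.625 (3.0/4.8), about 20% dropout, two-sided 0.05, about 80% power. SAP 4.2.6 and 4.10.8: 3 factors x 2 levels. SAP 4.2.5: 1 primary + 3 secondary endpoints.

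**Assumptions not in the documents.** Subgroup splits (50:50 unless stated), factors independent of each other, correlation among the four endpoints (0.3 to 0.8 unless stated), and two-sample t tests at Week 52 in place of the MMRM.

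**1. The plan's own figure.** 126 x 0.8 = 100.8 completers, or 67.2 and 33.6. A noncentral t gives 83.4% power (normal approximation 84.1%). The stated figure of about 80% is therefore a little conservative. Nothing below depends on the gap.

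**2. Count.** 3 x 2 x 4 = 24 comparisons at Week 52. This is a maximum, because small subgroups become descriptive.

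**3. Identical effect of 0.625 SD in every boy.** Each half has about 33.6 and 16.8 boys.
- SE = sqrt(1/33.6 + 1/16.8) = 0.299 SD; noncentrality = 0.625/0.299 = 2.09; power = 53.6%.
- Exactly one level significant: 2 x 0.536 x 0.464 = 49.7%.
- Unequal splits: 51% at 40:60 (power 45% and 62%) and 56% at 30:70 (35% and 68%).
- At least one of three factors split on NSAA: about 75% by simulation (101 boys, 67:34). Treating the factors as independent would give 1 - 0.503^3 = 87%. The true figure is lower because the same boys appear in every factor.

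**4. No effect anywhere.** If the 24 tests were independent, the chance of at least one p<0.05 would be 1 - 0.95^24 = 70.8%. They overlap, so simulation is needed (at least 5,000 trials per setting; ranges are across separate runs):

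| Endpoint correlation | Any of 24, either direction | Any of 24, favouring the drug |
|---|---|---|
| 0.3 | 59% | 33% |
| 0.5 | 54-56% | 29-30% |
| 0.8 | 42-43% | 21-23% |

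Stretching the correlation to 0 and 0.9 gives 61% and 37% in either direction, and 37% and 19% favouring the drug.

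For the six NSAA tests alone, about 21% of trials have at least one significant result in either direction and 10-12% have one favouring the drug. A non-significant primary together with an NSAA subgroup favouring the drug occurs in 8-9%.

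**5. What an interaction test would do.**
- False signals: 5% per factor by construction, about 14% over three NSAA factors, and about 44%, 39% and 30% over all 12 factor-endpoint pairs at correlation 0.3, 0.5 and 0.8.
- Power for a between-half difference of 0.625 SD (3 NSAA points): SE = 0.299 x sqrt(2) = 0.423; 0.625/0.423 - 1.96 = -0.48; power = 32%.

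**The case against.** The strongest reply is that no confirmatory claim is at risk. The hierarchy names four whole-population tests, and no subgroup result can become significant under that rule. The factors are prespecified stratification factors, not chosen after the fact. Undersized subgroups fall back to description. Section 4.10.8 states no alpha; 0.05 is read across from 4.2.1. Labels may also sit in the table shells, which are a separate document. All of this stands, and it confines the point to interpretation.

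A reader might go further and infer that a chance win for the drug is likely. The figures do not support that: the rates of 42-59% count results in either direction, and those favouring the drug are 21-33%. Nor will one level of a given factor usually be significant and the other not. At an even split that is a coin flip; only the any-of-three figure is about 75%.

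The remedy is not free of false signals either. Like for like, its 14% over three NSAA factors compares with about 75%, and over all 12 pairs it reaches 30-44%. Removing within-level p-values would not by itself help, since a 95% CI that excludes zero carries the same message. What remains unanswered is that nothing planned estimates the difference in effect between levels.

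**Conclusion.** The point holds as a weakness of method and reporting, not as a breach of error control. The planned analyses cannot show whether the effect differs by subgroup, and at this sample size they will often suggest a difference that does not exist: about 50% of trials per factor, and about 75% for at least one of three, under a uniform 0.625 SD effect. The chance of a favourable subgroup under no effect is real but smaller, at 21-33% over all 24 tests and 8-9% for a failed primary with a favourable NSAA subgroup.

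The reading of the text is firm. The sizes are approximate, since they rest on the assumed splits, correlations and independent factors, and on unadjusted t tests. Covariate adjustment in the MMRM would change the power in each level and so the disagreement rates.

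**What to change.** In SAP 4.10.8:

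1. For each factor, add treatment x subgroup and treatment x subgroup x visit terms to the 4.10.1 and 4.10.2 models on the whole FAP. Age and time to stand are continuous in those models, so their binary strata, with visit interactions, must be entered as well; region is already there. Report the Week 52 between-level difference in treatment effect with its 95% CI and a nominal interaction p-value.
2. Show within-level LS-means differences with 95% CIs as descriptive.
3. State that all subgroup and interaction results are exploratory and outside the 4.2.5 hierarchy.

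The cost is SAP wording and one extra model per factor and endpoint (12 in all), with no new data. There are two downsides to state. Interaction power is low, about 32% for a 3-point NSAA difference between halves, so a non-significant interaction is not evidence of a uniform effect; the CI should carry the interpretation. Unadjusted interaction tests also give false signals (about 14% over three NSAA factors, 30-44% over all 12 pairs), so the exploratory label must cover them too.

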4.11. Pharmacokinetic Analyses

Pharmacokinetic (PK) analyses will be described in a separate analysis plan.

4.12. Pharmacodynamic Analyses

Pharmacodynamic (PD) analyses may include evaluation of gene expression as well as circulating protein and micro-ribonucleic acid (RNA) biomarkers that help inform target engagement and efficacy. These assessments and blood samples will be collected at the times specified in [Table 1](#).

Descriptive statistics will be presented by treatment group for applicable PD endpoints and will be included as an appendix to the CSR (note: PD data may not be available at the time of database lock).

4.13. Safety Analyses

Safety analyses will be conducted using the Safety Population. Results of all safety assessments will be listed by patient, and summarized by treatment group and time point as applicable. These safety analyses will be compared qualitatively between treatment groups; however, there will be

no inferential statistical comparisons between groups (except for specific analyses, noted below).

4.13.1. Adverse Events

Adverse events will be coded using the MedDRA dictionary and displayed in tables and listings using System/Organ/Class (SOC) and Preferred Term (PT).

Analyses of adverse events will be performed for those events that are considered TEAEs, where treatment emergent is defined as any adverse event with onset after the administration of study medication through the end of the study (Week 52 visit) or any event that was present at Baseline but worsened in intensity or was subsequently considered drug-related by the investigator through the end of the study.

If the start date of an AE is partially or completely missing, then the date will be compared as far as possible with the date of the randomization. The AE will be assumed to be treatment emergent if it cannot be definitively shown that the AE did not occur or worsen during the post-randomization period (worst case approach).

The following general rules will be used:

- If the start day is missing, but the start month and year are complete, an AE will only be excluded as being on-study if the start month/year is before the month/year of randomization or if the stop date is before randomization.
- If the start day and month are missing, but the start year is complete, an AE will only be excluded as being on-study if start year is before the year of randomization or if the stop date is before randomization.
- If the start date is completely missing, an AE will be considered on-study unless the stop date is before randomization.

TEAE summaries will include the number and percentage of patients in each treatment group and overall. Summaries will include patients with:

- Any TEAEs
- Treatment-related TEAEs (Related, Possibly related)
- Maximum Severity of TEAEs
- Serious TEAEs, including any events resulting in death
- Treatment-related serious TEAEs
- TEAEs (and treatment-related TEAEs) leading to discontinuation of study drug

TEAEs are summarized by patient incidence rates, therefore, in any tabulation, a patient contributes only once to the count for a given adverse event (SOC or preferred term). TEAEs will also be summarized by SOC, PT, and severity and by SOC, PT, and relatedness. The most severe occurrence of a TEAE, as well as the most extreme relationship of the TEAE to the study procedure or treatment, will be used in tabulations of severity and relatedness in cases of multiple occurrences of the same TEAE.

Additionally, the prevalence of common treatment-related TEAEs will be summarized by treatment group and overall across the treatment period stratified into 4-week intervals. A common treatment-related TEAE is one which occurs in over 10% of the patients in either treatment group. The objective of this analysis is to determine the time course of the incidence of these TEAEs. The following are the 13 4-week intervals:

- 1) Baseline – Week 4 (i.e., Day 1 – Day 28)
- 2) Week 5 – Week 8 (i.e., Day 29 – Day 56)
- 3) Week 9 – Week 12 (i.e., Day 57 – Day 84)
- 4) Week 13 – Week 16 (i.e., Day 85 – Day 112)
- 5) Week 17 – Week 20 (i.e., Day 113 – Day 140)
- 6) Week 21 – Week 24 (i.e., Day 141 – Day 168)
- 7) Week 25 – Week 28 (i.e., Day 169 – Day 196)
- 8) Week 29 – Week 32 (i.e., Day 197 – Day 224)
- 9) Week 33 – Week 36 (i.e., Day 225 – Day 252)
- 10) Week 37 – Week 40 (i.e., Day 253 – Day 280)
- 11) Week 41 – Week 44 (i.e., Day 281 – Day 308)
- 12) Week 45 – Week 48 (i.e., Day 309 – Day 336)
- 13) Week 49 – Week 52 (i.e., Day 337 – Day 364)

For each interval, the percentage of patients with the treatment-related TEAE in the interval will be presented. For each interval, the denominator for the percentage will be the number of patients who were in the study for any part of that period (i.e., patients who discontinued from the study prior to the start of the interval will be excluded). For each related TEAE, a patient will be included in the numerator if any of the following criteria are met:

- The start date of the TEAE is in the interval
- The stop date of the TEAE is in the interval
- The start date of the TEAE is before the interval and the stop date is after the interval
- The start date of the TEAE is before the interval and TEAE is ongoing

Note: For this prevalence TEAE analysis, if the start day and/or month of the AE is missing, a value of 01 for the day and January for the month will be used. If the stop day and/or month of the AE is missing, December will be used for the month and the last day of the month will be used for the day.

All adverse events occurring on study will be listed in patient data listings.

By-patient listings also will be provided for the following: patient deaths; serious adverse events; and adverse events leading to discontinuation of study drug.

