#### 7.1.2. Adverse Events Occurring After Study Treatment

All AEs that occur from the time of the administration of the first dose of investigational product through the end of the safety follow-up will be considered treatment-emergent AEs (TEAEs).

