**APPENDIX 1. SCHEDULE OF ASSESSMENTS**

Study Week(s)	Screen a	BL b	Double Blind, Placebo-Controlled Treatment (Weeks 1 - 52)								Safety F/U c
	-4 - 0	0	6	13	19	26	32	39	45	52/ET d	
Informed Consent/Assent	X										
Site Visit e	X	X		X		X		X		X	
Site Call e, f			X		X		X		X		X
Med History/Demographics	X										
Confirm Eligibility	X	X									
Randomization g		X									
Vital Signs	X	X		X		X		X		X	
Weight	X	X		X		X		X		X	
Height		X				X				X	
Physical Examination	X	X		X		X		X		X	
AEs/Con Meds h	X		Continuous								
12-Lead ECG i	X					X				X	
Cardiac Monitoring j	X					X				X	
Hematology/Chemistry k	X	X		X		X		X		X	
ACTH/Cortisol k		X		X		X		X		X	
Urinalysis	X					X				X	
DNA Sample l		X									
Biomarkers, Gene Expression k		X		X		X		X		X	
NSAA, Stand from Supine, 10MWT, 4-Stair Climb, Muscle Strength m	X	X		X		X		X		X	
PUL n		X				X				X	
Videotape Functional Assessments o	X	X								X	
PODCI p		X								X	
Lateral Spinal Radiography, DXA q		X								X	
Study Drug Questionnaire						X					
Nutritional Guidance r		X									
Drug Dispensation		X		X		X		X			
Drug Accountability				X		X		X		X	
PK (plasma and urine) s				X		X				X	

a Per Investigator's discretion, informed consent, medical history/demographic data and lab assessments may be completed remotely by a qualified medical professional.

b The first day of study drug is "Day 1"; unless otherwise specified, all assessments should be completed within a 4 week window prior to Day 1.

c Safety follow-up should occur within 2 wks. after last dose of study drug. Patients continuing in the open-label extension study are not required to perform the safety follow-up.

d If patient discontinues treatment early, patient will be asked to return for early termination (ET) visit prior to their last dose of study drug. Functional assessments performed within 6 weeks of discontinuing treatment do not need to be repeated at the ET visit. If the ET visit occurs after drug has been discontinued, certain assessments may be omitted per Sponsor discretion.

- e Weeks 6-19 should be conducted within the study week with a  $\pm 4$ -day window. Weeks 26-54 have a  $\pm 10$ -day window.

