2. STUDY DESIGN

2.1. Synopsis of Study Design

This is a randomized, double-blind, placebo-controlled, Phase 3, multisite study of edasalonexent in pediatric patients with DMD.

[figure not shown]
Eligible patients will be ambulatory boys aged ≥ 4.0 to < 8.0 years with a confirmed diagnosis of DMD who have not use steroids within 24 weeks prior to treatment start (Day 1). In regions where eteplirsen is approved or there is an established access program, patients who have received at least 24 weeks of treatment with eteplirsen prior to Day 1 will be eligible.

As shown in [Figure 1](#), following a 4-week screening period to determine eligibility, approximately 126 patients will be randomized 2:1 to receive edasalonexent 100 mg/kg/day or placebo in a double-blind fashion daily for 52 weeks. Randomization will be stratified by baseline age (≤ 6.0 vs. > 6.0 years), baseline time to stand from supine (≤ 5 vs. > 5 seconds), treatment with eteplirsen (yes vs. no), and region (North America vs. Europe/Asia/Australia). Note that if siblings are enrolled, they will be assigned to the same treatment group.

Randomized patients (and enrolled siblings who are not randomized) will complete Baseline procedures and begin receiving study drug (edasalonexent or placebo) on Day 1. During the treatment period, patients will have site visits approximately every 13 weeks with site calls in between as specified in the Schedule of Assessments ([Table 1](#)). For those patients who do not enter the extension study, a safety follow-up should occur within 2 weeks of the last dose of study drug for collection of adverse events (AEs).

The length of a patient's participation in the study will be from the time of informed consent through the Week 52 visit. A patient will be considered to have completed the study when they have completed the Week 52 assessments. Patients who do not participate in the open-label extension study will be considered to have completed the study after they complete the safety follow-up.

Figure 1 Overview of Study Design

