6. CHANGES TO PLANNED ANALYSES

The following are changes to the planned analyses as specified in the 16APR2020 version of the protocol:

- The MMRM model for the primary and secondary endpoint analyses was updated to include baseline covariate by study visit interaction terms and the Baseline age and Baseline time to stand are continuous variables (as specified in [Section 4.10.1](#)).
- An additional endpoint was added, the CFB rank sum score at Week 52. This endpoint is designed to assess the effect of edasalonexent versus placebo across multiple endpoints using a non-parametric rank-based approach. The endpoint is the sum of the ranks of the following Week 52 CFB scores: NSAA, 10MWT speed, stand from supine speed, 4-stair climb speed, and PODCI transfer and basic mobility scale.

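### SAP 4.13.1 closes the treatment-emergent AE window at the Week 52 visit, Protocol 7.1.2 closes it at the end of the safety follow-up, and SAP Section 6 does not declare the difference

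*SAP*

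**What the plan says.** Protocol Section 7.1.2 starts the treatment-emergent period at the first dose and counts AEs "through the end of the safety follow-up will be considered treatment-emergent AEs (TEAEs". The protocol's AE analysis section (9.12.3) gives no other window.

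SAP Section 4.13.1 restricts AE analyses to TEAEs and defines one as "any adverse event with onset after the administration of study medication through the end of the study (Week 52 visit". A second limb covers baseline events that worsen or are later judged drug-related; it also runs to the end of the study.

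SAP Section 2.1 makes two statements about completion. One ties participation and completion to Week 52. The next reads: "Patients who do not participate in the open-label extension study will be considered to have completed the study after they complete the safety follow-up". Protocol Section 3.3.3.1 has the same pair. SAP 2.1 also gives the purpose of the contact for boys not entering the extension: "a safety follow-up should occur within 2 weeks of the last dose of study drug for collection of adverse events (AEs". The protocol's schedule shows it as a site call, and its footnote c adds: "Patients continuing in the open-label extension study are not required to perform the safety follow-up".

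SAP Section 6 opens with "The following are changes to the planned analyses as specified in the 16APR2020 version of the protocol". Two items follow, the revised MMRM model and the added rank sum endpoint. Neither concerns TEAEs, and the version history in SAP 1.2 records no change of window.

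**The concern.** The two documents give different end days for the same flag, and nothing shows that the change was intended. Safety and tolerability is a secondary objective (Protocol 3.2), and the TEAE tables are its main between-group summary. Protocol Section 7 has AEs recorded through follow-up, so the data will exist. Under the SAP rule, an event that starts after the Week 52 visit and is reported at the call drops out of every TEAE table, including those for serious and treatment-related events. What is at stake is agreement between the protocol and the reported tables, and a single reproducible rule for whoever programs the flag.

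**Working it through.** The documents state no figure to reproduce here. The check is a comparison of texts plus the length of the gap.

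**Step 1: end day for boys not entering the extension.**
- Protocol 7.1.2: the end of the safety follow-up.
- SAP 4.13.1: the end of the study, with a parenthesis naming the Week 52 visit.
- SAP 2.1: the end of the study could be either the Week 52 assessments or the follow-up. The phrase alone is therefore ambiguous for these boys. The parenthesis in 4.13.1 settles it, against the protocol.

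**Step 2: declared or not.** SAP Section 6 has two items, neither on TEAEs. The change is undeclared.

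**Step 3: length of the gap.** Inputs:
- nominal Week 52 day = 364 (SAP 5.2; the last 4-week AE interval in SAP 4.13.1 also ends at Day 364)
- follow-up at d days after the last dose, 0 ≤ d ≤ 14 (SAP 2.1; Protocol Appendix 1, footnote c)
- assumption: the last dose is on the Week 52 visit day

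Gap = (364 + d) − 364 = d, so 0 to 14 days.

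Longest protocol window = 364 + 14 = 378 days. Largest share omitted = 14 / 378 = 0.037, or 3.7%.

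If COVID-19 delays the Week 52 visit (Protocol Appendix 2), both end days move with it. The 14-day limit stays and the share falls slightly.

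**Step 4: boys entering the extension.** They need no follow-up call, so the gap is 0 days.

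**Step 5: how many boys.** The documents do not give the number who decline the extension. For illustration only, if a share p of 126 boys complete Week 52 and decline, the boys affected are 126p and the most person-days outside the SAP window are 126p × 14:
- p = 5%: 6.3 boys, 88 person-days
- p = 10%: 12.6 boys, 176 person-days
- p = 50%: 63 boys, 882 person-days

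These are upper limits on time at risk, not counts of missed events.

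**Step 6: which events are affected.** The SAP's rules for partly or wholly missing start dates test only against randomization and set no upper limit. An AE with an incomplete start date can therefore still be flagged. The omission applies to AEs whose start date is known to fall after the Week 52 visit.

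**The case against.** The strongest reply is that the Week 52 end is a defensible choice with little consequence. It follows one of the two completion statements in SAP 2.1 and Protocol 3.3.3.1. It gives completers the same visit-based end whether or not they enter the extension. The events are not lost: "All adverse events occurring on study will be listed in patient data listings", and deaths, serious AEs and AEs leading to discontinuation have their own listings. AE comparisons between arms are qualitative, so no test is affected.

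Most of this stands, and it is why the point is minor. It does not remove the conflict with Protocol 7.1.2, and a deliberate choice of this kind belongs in SAP Section 6 with a reason.

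Three stronger readings are tempting but not supported:
- A reader might infer that SAP 4.13.1 flatly contradicts SAP 2.1. It does not. SAP 2.1 carries both completion statements, and 4.13.1 follows one of them.
- A reader might infer that, for boys who leave early, the window closes before the last dose. The schedule has one column for Week 52 and early termination, and footnote d says the "patient will be asked to return for early termination (ET) visit prior to their last dose of study drug". But SAP 4.13.1 does not say that the early termination visit ends the TEAE window. Where the SAP wants that visit to stand in for a scheduled one, it says so (4.2.10 for visit mapping, 4.9 for exposure). Nor can the planned 20% dropout be used to count such boys. Protocol 5.2.5 separates stopping treatment from leaving the study, and 7.1.3 keeps recording AEs in boys who stay.
- A reader might infer that the 4-week prevalence table must be extended past Day 364. The SAP describes that table as covering the treatment period, so it can stay.

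**Conclusion.** The concern holds as a minor inconsistency between the protocol and the SAP. Following the SAP as written, AEs with a known onset after the Week 52 visit are left out of the TEAE tables for boys who do not enter the extension, although the protocol counts them. The size is at most 14 of about 378 days (3.7%) per affected boy, assuming the last dose is on the Week 52 visit day and the call is made within its two-week limit. The number of boys affected is unknown. The same rule applies to both arms, so nothing in the wording itself favours one of them.

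**What to change.** In SAP 4.13.1, replace the Week 52 end of the TEAE window with these end days, use them for the worsening limb as well, and set the TEAE flag to match:
- the end of the safety follow-up, as in Protocol 7.1.2;
- the Week 52 visit for boys entering the extension, who have no safety follow-up;
- study completion for boys who stop drug but remain in the study, in line with Protocol 7.1.3.

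If the sponsor prefers the shorter window, the alternative is to declare it in SAP Section 6 with a reason.

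The cost is one sentence and a small change to the flag's program. No visit, call or data item is added. The downside is that boys who decline the extension have a TEAE window up to 14 days longer than boys who enter it. A footnote to the TEAE tables should state the window for each group.
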